9.5.6 Pharmacokinetics Analysis

PK analysis will be carried out for subjects in the dose-escalation study and in the efficacy study with blood samples collected at defined timepoints as listed in section 0. The PK analysis will be PP. The following PK analysis will be performed as needed.

Individual Subject Pharmacokinetic Analysis: A non-compartmental (NC) PK analysis will be performed on the L9LS concentration data generated from each subject. Individual subject and dosing arm concentration-versus-time profiles will be constructed in linear and semi-log scales. In the NC analysis, the maximum concentration (Cmax) and time of maximal concentration (Tmax) will be taken directly from the observed data. The area under the concentrations vs. time curve (AUC) will be calculated using the trapezoidal method and determined out to the final concentration collected. If a subject's L9LS concentration falls below the quantitative limit (QL) of the assay, the sample with concentration below the QL will be assigned a L9LS concentration value of "0" for AUC calculations. In addition to the total AUC, partial AUCs will also be determined over certain time intervals. The time-weighted average concentrations (Cave) during these intervals will be calculated as the AUC divided by the AUC collection interval (e.g., Cave_{0-16WK} = (AUC_{0-16WK}) / 16 weeks). The terminal slope, λ_z , will be determined by regression of the

terminal, log-linear portion of the concentration-versus-time profile. If the final PK sample has measurable L9LS concentrations greater than the assay QL, the AUC post-final PK collection (AUC_{last-infinity}) will be estimated as C_{last} / λ_z and $AUC_{0-infinity}$ will be calculated as the sum of $AUC_{0-last} + AUC_{last-infinity}$.

Population Pharmacokinetic Analyses: Based on preclinical PK results for L9LS and known PK behavior studies of MAbs, the two-compartment model will be used for population PK analysis. The population analysis will estimate compartmental PK parameters such as the clearance (CL), central and peripheral volumes of distribution (Vd1 and Vd2), and intercompartmental clearance (Q). Total volume of distribution at steady-state (Vdss), will be calculated as the sum of Vd1 + Vd2. Alpha and beta half-lives will be calculated from CL, Q, Vd1, and Vd2 using standard equations. ³⁷

To assess the association of L9LS concentration with protection, we will perform a Cox proportional hazards regression for the time to the first infection with L9LS concentration as a time-varying covariate. A logistic regression analysis will be additionally performed to model the infection rate as a function of L9LS concentration using generalized estimating equation to account for repeated measures. This analysis will be performed over all participants that receive L9LS including those aged 5-10 years in the dose-escalation study and those in the efficacy study.

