9.2.2 Sample Size Considerations for the Efficacy Study

Table 6 shows initial sample size estimations powered to detect a 70% vaccine efficacy (1 – [proportion infected in L9LS/proportion infection in control]) at 12 months comparing L9LS at 10-20 mg/kg to placebo. Sample size calculations were done assuming the endpoint of any Pf infection will be calculated using a proportional analysis, 80% or 90% power, an alpha of 0.05, and that either 30%, 35%, or 40% of children in the placebo group are infected at 6 months and that 40% or 45% are infected at 12 months. (Time-to-event analyses typically require smaller sample sizes.) The primary endpoint will be at 12 months and will combine both MAb age groups who received two doses of L9LS and compare those subjects to the overall placebo group, i.e., we will assess MAb efficacy among children 5–59 months. However, the trial sample size is based on the secondary endpoint of 12-month MAb efficacy with two doses among the younger age group (5–17 months) versus the 5–17-month-old subjects in the placebo group, as these will require larger sample sizes than the primary endpoint. Factoring in 25% loss to followup over 12 months, and a doubling of the sample size in each intervention arm to allow for comparison of L9LS with a second dose (at 6 months) to placebo and comparison of L9LS without a second dose to placebo would require 108 children in each L9LS group and 54 children in the placebo arm, assuming 35% infected in the placebo group at 6 months.

Abbreviated Title: Anti-malaria MAb in Kenyan children

Version 6.0 Date: 2 Apr 2024

Table 6. Sample size calculations based on secondary 12-month endpoint, to achieve 80% power to detect efficacy of 70% at 6 months and 60% at 12 months, assuming 35% of the control group are infected by 6 months and 45% by 12 months.

| Arm | Assumed proportion infected in control group by 6 mos | mAb Efficacy at 6 months | Power | Number needed at 6 months | | Assumed % infected in control group by 12 mos | mAb Efficacy at 12 months | Number needed at 12 months | Number needed to enroll | Number with 20% LTFU* |
|------------------------------|---|-----------------------------------|----------|---------------------------------|-----|---|------------------------------------|-------------------------------------|-------------------------------|-----------------------|
| mAb 5-17 mos + Dose 2 | 0.30 | 70% | 80% | 50 | 120 | 0.40 | 60% | 52 | 104 | 130 |

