9.4 Populations for Analyses

The following datasets will be considered in study analyses:

- Intention-to-treat (ITT) analysis dataset will include all subjects that are randomized and will be analyzed according to the initial randomization assignment.
- Modified intention-to-treat (MITT) analysis dataset will include all randomized subjects that receive the study intervention and will be analyzed according to the initial randomization assignment.
- Per-protocol (PP) analysis dataset will include all randomized subjects that receive the study intervention consistent with the initial randomization assignment and complete the scheduled visits, and will be analyzed according to the initial randomization assignment.
 In cases where subjects receive an intervention other than the one randomly assigned, an as-treated analysis will be additionally performed according to the actual product received.

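### The PK analysis is limited to children who complete the scheduled visits, which would drop about 39–50 part 2 children who have usable post-dose concentrations

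*Combined protocol and SAP*

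**What the plan says.** Section 9.5.6 fixes the PK population in one sentence: "The PK analysis will be PP". Section 9.4 defines the per-protocol (PP) set as randomised children who "receive the study intervention consistent with the initial randomization assignment and complete the scheduled visits". Neither section says how many visits may be missed before a child stops counting as having completed them.

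Two other statements in section 9.5.6 point to wider sets. The non-compartmental analysis is to be "performed on the L9LS concentration data generated from each subject", with AUC taken to the last concentration collected. For the Cox and logistic models that relate concentration to infection, the section says "This analysis will be performed over all participants that receive L9LS", with no condition on visits.

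On expected loss, the text of section 9.2.2 allows for "25% loss to followup over 12 months", while the last column of Table 6 is labelled "Number with 20% LTFU". Section 9.3 uses 20% for the extension.

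The part 2 schedule (section 1.4.2) has PK draws at pre-enrolment and then at days 28, 196 and 336, with dosing at days 0 and 168.

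**The concern.** Visit completion is a sensible filter when the question is whether a regimen works if followed. It is a poor filter for PK. What makes a concentration interpretable is the product and dose received and the time of the draw, and missing a later visit changes none of these. A child lost at month 9 has valid day 28 and day 196 concentrations, and under the rule as written both are set aside. Part 2 has only three post-dose draws per child, so there is little data to spare.

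PK is secondary objective 7 in part 2 and a primary objective of the extension. Section 4.2.2 also uses half-life and time to undetectable concentration in its case for the extension dose range, so these estimates inform decisions. The efficacy analysis (9.5.4) and the main safety analysis (9.5.5) are both modified intention-to-treat; PK alone is tied to completion.

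The mismatch of populations adds a problem of interpretation. PK parameters would come from completers and the concentration–protection estimates from all recipients, so a reader putting them together would be combining results from different groups of children.

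**Working it through.** **Inputs**
- L9LS children in part 2: 108 in each of two age groups, so 216 (section 9.2.2, Table 1).
- Loss over 12 months: d = 0.20 (Table 6 column, section 9.3) or 0.25 (section 9.2.2 text).
- Post-dose PK draws: days 28, 196 and 336 of a 364-day follow-up (section 1.4.2).
- Assumption, since the documents give no timing of loss: constant hazard over the year. Straight-line loss is shown as a check.

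**The plan's own figure.** For 45% versus 18% infected, two-sided alpha 0.05 and 80% power, with unpooled variance: n = (1.96 + 0.8416)² × (0.45×0.55 + 0.18×0.82) / 0.27² = 42.5, rounded up to 43, as in Table 6. Then 43/0.80 = 53.75, giving 54, and 86/0.80 = 107.5, giving 108. The enrolment numbers therefore match a 20% loss. A 25% loss handled the same way would give 58 and 115; 54 and 108 arise from 25% only as a multiplication by 1.25. Both rates are carried below.

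**Children excluded.** 216 × 0.20 = 43.2 and 216 × 0.25 = 54. The PP set keeps about 173 or 162.

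**Excluded children who hold a valid sample.** The number lost after day t is 216 × [(1−d)^(t/364) − (1−d)]. Straight-line loss gives 216 × d × (364−t)/364.

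| Lost after | d = 0.20, constant hazard | d = 0.20, straight line | d = 0.25, constant hazard | d = 0.25, straight line |
|---|---|---|---|---|
| Day 28 | 39.5 | 39.9 | 49.3 | 49.8 |
| Day 196 | 18.7 | 19.9 | 23.0 | 24.9 |
| Day 336 | 3.0 | 3.3 | 3.6 | 4.2 |

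So about 39–50 of the 43–54 excluded children, some 91–92%, have at least one post-dose concentration. The rest leave before day 28 and no definition could recover them.

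**Samples discarded.** Under constant hazard, the unrounded column sums are 61.3 (20%) and 75.9 (25%). Obtainable samples are those from completers plus these: 3 × 172.8 + 61.3 = 579.7, and 3 × 162 + 75.9 = 561.9. The shares discarded are 10.6% and 13.5%.

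**Precision.** Treating precision as proportional to the number of samples: 1/√(1 − 61.3/579.7) = 1.06 and 1/√(1 − 75.9/561.9) = 1.08. Intervals widen by about 6–8%. Straight-line loss gives the same rounded range.

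**Stricter reading of completion.** Section 7.3 counts a child as lost only after three consecutive missed visits without contact, whereas PP asks for the scheduled visits to be completed. For illustration only, with an assumed independent miss rate of 1–3% per visit over 14–18 visits, the share attending every visit runs from 0.97^18 = 58% to 0.99^14 = 87%. Read strictly, the rule could therefore exclude many more children than loss to follow-up alone.

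**The case against.** Several points on the other side are fair.

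- **Separate populations for separate analyses.** A reader might infer that section 9.5.6 contradicts itself. It need not. The PP sentence can be read as governing the non-compartmental and population PK analyses, with the closing paragraph setting its own, broader set for a different analysis. That stands. On this reading the concentration–protection work already uses the wider group.
- **No stated model link.** A reader might also infer that the concentration–protection models take their input from the PK model. The documents do not say so. Section 9.5.6 enters concentration as a time-varying covariate, and section 8.2.3 uses the concentration at the visit before first infection. The harm is a difference in who is described, not a broken input.
- **Wrong product.** It would be too strong to say that PK from a child given the wrong product is simply lost. The PP paragraph in section 9.4 itself adds an as-treated analysis for such children. It does nothing for incomplete follow-up.
- **Size.** Counting children instead of samples gives 1/√0.80 = 1.12 and 1/√0.75 = 1.15, a widening of 12–15%. That overstates the loss, because a child who leaves early would have contributed fewer samples than a completer. The 20–25% is also a planning allowance, not observed loss.
- **Bias.** Nothing in the documents ties visit completion to clearance or volume of distribution, so bias in the PK estimates is not shown.
- **One sample is not enough for everything.** A single concentration cannot support a terminal slope or an AUC to infinity. That stands and shapes the remedy.
- **A later analysis plan.** Section 9.5 announces a detailed plan that will supersede the protocol. Its content is not in these documents, and the PP sentence is the only PK population rule they give. The later plan is a convenient place for the repair, not evidence that it has been made.

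**Conclusion.** The concern holds as an avoidable loss of data and a mismatch between analysis sets. Followed as written, the plan excludes about 43–54 of 216 part 2 L9LS children from PK. About 39–50 of them hold at least one valid post-dose concentration, and 61–76 samples are discarded. The cost in precision is modest, about 6–8% on a sample-count basis. It would be larger if a single missed visit disqualifies a child.

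The figures rest on the plan's own 20–25% allowance, on loss spread evenly or at constant hazard over the year, and on sample count as a rough stand-in for information; precision also depends on the number of children. They cover part 2 alone. The 54 part 1 L9LS recipients (section 2.3.1) are followed for three months, have no stated loss rate and are not in the count. Section 9.5.6 names only the dose-escalation and efficacy studies, so no figure is given for the extension.

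**What to change.** - **Population PK:** define the set as all L9LS recipients with at least one evaluable post-dose concentration, analysed by actual product, dose and sampling time. This brings it into line with the set used for the concentration–protection models.
- **Non-compartmental parameters:** include each child whose samples support the parameter in question, whether or not later visits were completed. For the terminal slope, that means stating how many terminal-phase samples are enough.
- **PP:** keep it as a sensitivity analysis, and state what completing the scheduled visits means, including how many missed visits are tolerated.

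The change fits in section 9.5.6 or the later analysis plan and should be settled before unblinding. It needs no new visits, samples or participants. The small cost is writing a parameter-specific evaluability rule and slightly more analysis work.

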⁹ Half of the participants will have this blood draw on Day 28 and the other half will have it at Day 84. Accordingly, the total cumulative volume reflects a PK blood volume for Day 28 or Day 84, but not both.

| Study Time | point | Screen ⁰ | Pre- Enrollment ⁰ | Enrolment | D1 1 | D3 ¹ | D7 | D28 (Wk 4) | D56 (Wk 8) | D84 (Wk 12) | D112 (Wk 16) | D140 (Wk 20) | D168 (Wk 24)* | D169 1 | D171 ¹ | D175 | D196 (Wk 28) | D224 (Wk 32) | D252 (Wk 36) | D280 (Wk 40) | D308 (Wk 44) | D336 (Wk 48) | D364 (Wk 52) | Unscheduled Visit ² |
|---|----------|---------------------|---------------------------------|-----------|--------|-----------------|-----|------------|------------|-------------|--------------|--------------|---------------|--------|-------------------|------|--------------|--------------|--------------|--------------|--------------|--------------|--------------|-----------------------------------|
| Window (da | ays) | -56 to -14 | -21 to -14 | - | +1 | ±1 | ±1 | ±7 | ±7 | ±7 | ±7 | ±7 | ±7 | +1 | ±1 | ±1 | ±7 | ±7 | ±7 | ±7 | ±7 | ±7 | ±7 | uled |
| Concomitant medications ³ | | | X | X | X | X | X | X | X | X | X | X | X | X | X | X | X | X | X | X | X | X | X | X |
| Dihydroartemis piperaquine administration | sinin- | | X 4 | | | | | | | | | | | | | | | | | | | | | |
| Randomization | | | | X | | | | | | | | | | | | | | | | | | | | |
| Study agent administration | | | | X 5 | | | | | | | | | X 5 | | | | | | | | | | | |
| Adverse events | \$ | | X | X | X | X | X | X | X | X | X | X | X | X | X | X | X | X | X | X | X | X | X | |
| Labora | tory Ev | aluat | ions | | | | | | | | | | | | | | | | | | | | | |
| Test | Tube | | (Blo | od vo | lume i | n mL) |) | | | | | | | | | | | | | | | | | |
| HIV ⁶ | SST | | 0.2 | | | | | | | | | | | | | | | | | | | | | |
| CBC with differential | EDT A | | 0.1 | 0.1 | | | 0.1 | 0.1 | | | | | 0.1 | | | 0.1 | | | | | | 0.1 | | |
| Hemoglobin type | EDT A | | 0.5 7 | | | | | | | | | | | | | | | | | | | | | |
| ALT, Cr | SST | | 0.2 | 0.2 | | | 0.2 | 0.2 | | | | | 0.2 | | | 0.2 | | | | | | 0.2 | | |
| Blood smear and dried blood spot for Pf RT-PCR | - | | 0.4 | 0.48 | | | 0.4 | 0.4 | 0.4 | 0.4 | 0.4 | 0.4 | 0.4 | | | 0.4 | 0.4 | 0.4 | 0.4 | 0.4 | 0.4 | 0.4 | 0.4 | 0.4 |
| PK studies | SST | | 3.1 9 | | | | | 3.1 | | | | | | | | | 3.1 | | | | | 3.1 | | |

Version 6.0 Date: 2 Apr 2024

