2.2.1.3 Clinical Experience

L9LS was evaluated in a phase 1, dose-escalation, open-label clinical trial with experimental CHMI to evaluate safety and protective efficacy of L9LS in healthy, malaria-naive adults at the VRC. The phase 1 trial at the VRC was a two-part, dose-escalation, adaptive-design study evaluating the safety, tolerability, PK, and protective efficacy of L9LS.

Doses evaluated ranged from 1 to 20 mg/kg delivered via IV administration, and 5 mg/kg delivered via SC administration. No safety concerns were identified. A total of 17 L9LS recipients and 6 control participants underwent CHMI. Of the 17 participants who received a

single dose of L9LS, 15 (88%) were protected after CHMI. Parasitemia did not develop in any of the participants who received 5 or 20 mg/kg of IV L9LS. Parasitemia developed in 1 of 5 participants who received 1 mg/kg IV, 1 of 5 participants who received 5 mg/kg SC, and all 6 control participants through 21 days after CHMI. Protection conferred by L9LS was seen at serum concentrations as low as 9.2 µg/mL. Thus, in this small phase 1 trial, L9LS administered IV or SC protected recipients against malaria after controlled infection, without evident safety concerns, and all IV and SC administrations were well tolerated. 15

For the first proof-of-concept study with CIS43LS in Malian adults, CIS43LS was administered by the IV route at doses of 40 mg/kg and 10 mg/kg. The first generation anti-malaria MAb CIS43LS was shown to be safe and conferred complete protection against controlled Pf infection in a phase 1 study in healthy adult volunteers at the VRC. CIS43LS was evaluated in a completed phase 2 study of adults in Mali (ClinicalTrials.gov Identifier: NCT04329104). For the first proof-of-concept study with CIS43LS in Malian adults against intense seasonal transmission, CIS43LS was administered by the IV route at doses of 40 mg/kg and 10 mg/kg. No significant safety concerns were noted. By time-to-event analysis, compared to placebo at 6 months, CIS43LS efficacy was 88.2% (adjusted 95% CI, 79.3 to 93.3; P<0.0001) for 40 mg/kg, and 75.0% (adjusted 95% CI, 61.0 to 84.0; P<0.0001) for 10 mg/kg Together, the phase 1 and 2 trials of CIS43LS provide proof of concept that a MAb with an extended half-life can safely confer protection against Pf infection.

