6 STUDY INTERVENTION

6.1 Study Interventions(s) Administration

6.1.1 Study Intervention Description

The study intervention involves an initial administration of L9LS SC or placebo SC to all subjects. At six months, subjects in part 2 of the study will receive either a second dose of L9LS (half those in MAb groups) or placebo (other half of those in MAb groups and those in placebo group). During the part 2 extension, participants will receive 2 additional SC doses (either two of L9LS, one of L9LS and one of placebo, or two of placebo), 6 months apart, following their initial randomization.

6.1.2 Dosing and Administration.

Study agent and dosing will be dependent on the progress of the study and study arm assignment (Table 1). Total effective doses by subject weight for part 2 of the study are provided in Table 2 (section 6.2.4). The dose escalation study dosing plan is described in section 0. Procedures for administration are described in section 6.1.2.4.

Table 1. Study agent assignment and dosing by age group/arm

| | Total | | | | | |
|----------------|----------|---|--|--|--|--|
| Age group/arm | Subjects | Study Agent and Dose | | | | |
| | Part 1 | | | | | |
| | 12 | 5 mg/kg L9LS SC (n=9) or placebo SC (normal saline; n=3) | | | | |
| 5 to 10 years | 12 | 10 mg/kg L9LS SC (n=9) or placebo SC (normal saline; n=3) | | | | |
| | 12 | 20 mg/kg L9LS SC (n=9) or placebo SC (normal saline; n=3) | | | | |
| | 12 | 5 mg/kg L9LS SC (n=9) or placebo SC (normal saline; n=3) | | | | |
| 5 to 59 months | 12 | 10 mg/kg L9LS SC (n=9) or placebo SC (normal saline; n=3) | | | | |
| | 12 | 20 mg/kg L9LS SC (n=9) or placebo SC (normal saline; n=3) | | | | |

| | Part 1b | | | | | |
|--------------------------------|---------|--|--|--|--|--|
| 5 to 71 months | 12 | 30 mg/kg L9LS SC (n=9) or placebo SC (normal saline; n=3) | | | | |
| 12 | | 40 mg/kg L9LS SC (n=9) or placebo SC (normal saline; n=3) | | | | |
| | | Part 2 | | | | |
| Arm 1 (5 to 17 months of age) | 108 | 10-20 mg/kg L9LS SC plus second dose of 10-20 mg/kg L9LS SC or second placebo dose at 6 months | | | | |
| Arm 1 (18 to 59 months of age) | 108 | 10-20 mg/kg L9LS SC plus second dose of 10-20 mg/kg L9LS SC or second placebo dose at 6 months | | | | |
| Arm 2 (5 to 59 months of age) | 108 | Placebo (normal saline) SC plus second dose of placebo at 6 months | | | | |
| | | Part 2 Extension (year 2) | | | | |

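### Section 9.5.6 promises two-compartment parameters (CL, Vd1, Vd2, Q, Vdss, alpha half-life) that subcutaneous-only data, first sampled post-dose on day 7 or day 28, cannot deliver; exposure from day 7 remains estimable, so severity is low

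*Combined protocol and SAP*

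**What the plan says.** The population PK paragraph of section 9.5.6 fixes the structure: "the two-compartment model will be used for population PK analysis". It then lists the parameters, with Q as the last item: "The population analysis will estimate compartmental PK parameters such as the clearance (CL), central and peripheral volumes of distribution (Vd1 and Vd2), and intercompartmental". For Vdss, the plan is that it "will be calculated as the sum of Vd1 + Vd2", and for the half-lives: "Alpha and beta half-lives will be calculated from CL, Q, Vd1, and Vd2". No absorption rate, lag or bioavailability is mentioned, and no parameter is described as apparent.

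On route, section 6.1.1 says: "The study intervention involves an initial administration of L9LS SC or placebo SC to all subjects". The later doses are subcutaneous too, and no arm receives L9LS intravenously.

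On sampling, the schedules in sections 1.4.1 and 1.4.3 (parts 1 and 1b) give a pre-dose sample, then day 7, then day 28 for half the children and day 84 for the other half. Sections 1.4.2 and 1.4.4 (part 2 and extension) give a pre-dose sample, then days 28, 196 and 336, with the second injection at day 168. There is no PK sample on day 0 after dosing, day 1 or day 3 in any part.

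Intravenous data exist elsewhere. Section 2.2.1.3 says of the phase 1 trial: "Doses evaluated ranged from 1 to 20 mg/kg delivered via IV administration, and 5 mg/kg delivered via SC administration". Section 9.5.6 does not say that these data will be used.

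**The concern.** The listed quantities describe disposition after a dose of known size has reached the circulation. After a subcutaneous dose the absorbed fraction F is unknown and the input is slow. Absolute CL, Vd1, Vd2, Q and Vdss then cannot be recovered without intravenous data. Separating absorption from distribution also needs samples in the first days, and none are taken.

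An analyst who follows the text would report volumes, an intercompartmental clearance and an alpha half-life that reflect starting values and software settings more than the children's data. Readers could take these as paediatric L9LS parameters and carry them into later dose modelling.

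**Working it through.** The documents give no precision target for the PK model, so there is no figure to reproduce.

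**Inputs from the documents**
- L9LS recipients: 54 in part 1 (section 2.3.1) plus 2 × 9 = 18 in part 1b (Table 1), total 72. Part 2: 2 × 108 = 216 (Table 1). Extension: 216 × 0.80 ≈ 173, using the 20% loss in section 9.3.
- Sample days and windows: sections 1.4.1 to 1.4.4 (±2 days at day 7 in parts 1 and 1b, ±7 days at the other PK visits).
- Terminal half-life about 35 days in Malian children, and detection limit 0.61 µg/mL (section 4.2.2).

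**Assumptions not in the documents:** ka 0.15 to 0.5/day; Q 4 to 12 mL/day/kg; V1 = V2 = 45 mL/kg (50 mL/kg in steps 1, 2 and 4); alpha half-life 1 to 3 days in step 2; F 0.5 to 0.9; between-child SD (log scale) 0.3 on CL and V1 and 0.5 on ka; residual error 20%.

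**Step 1, structure.** With first-order input, C(t) = (F·D·ka/V1)·g(t; ka, CL/V1, Q/V1, Q/V2). Multiplying F, CL, Q, V1 and V2 by one constant leaves C(t) unchanged. Example: F from 0.7 to 0.5 is a factor of 0.714, and CL goes from 0.002118 to 0.001513 L/day/kg. The largest relative difference in concentration is 1e-14. Absolute CL, Vd1, Vd2, Q and Vdss are thus known only relative to F, whatever the sample size. Half-lives are unaffected, because F cancels.

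**Step 2, what the first sample can see.**
- Absorbed by day 7 = 1 − exp(−7·ka): 65% at ka = 0.15 and 88% at ka = 0.3.
- Alpha term remaining at day 7 = 0.5^(7/half-life): 0.8% for 1 day and 20% for 3 days.
- By day 28 at least 98% is absorbed, and at most 0.5^(28/3) ≈ 0.2% of the alpha term remains.

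Only the single day-7 sample from the 72 children in parts 1 and 1b carries early information, and there absorption and distribution are mixed.

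**Step 3, precision.** First-order expected information on log parameters: M = Σ J′V⁻¹J, where J is the derivative of log C, V = JΩJ′ + σ²I, and RSE = 100·√diag(M⁻¹). Nine ka × Q scenarios, terminal half-life about 37 days, F fixed so that parameters are apparent, ka estimated, visits spread evenly over their windows, values below 0.61 µg/mL dropped.

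| Quantity | RSE over the nine scenarios |
|---|---|
| Vd1/F, Vd2/F | 23% to about 5,000% |
| Q/F | about 40% to 4,600% |
| CL/F | 2% to 13% |
| Terminal half-life | 1.6% to 3.7% |

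Vd1/F, Vd2/F and Q/F all exceed 130% in seven of the nine scenarios and lie between 83% and 102% in an eighth. Small changes in set-up move the first count to eight. If every visit fell on its nominal day, the five-parameter matrix would be near-singular. With ka, Q/F and V2/F fixed from outside, CL/F and V1/F are each estimated to about 2% to 3%.

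**Step 4, the text taken literally** (no absorption, F = 1), fitted to noise-free subcutaneous data. Fitted CL is 1.05 to 1.93 times the true value for F from 0.9 to 0.5. At F = 0.7, fits of nearly equal quality give alpha half-lives from 0.0015 to 17 days, while the terminal half-life is 35.0 days in each.

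**Step 5, does it reach the exposure predictions?** In the step 3 set-up, the RSE of the typical predicted concentration is at most 8.2% on the days checked from day 7 to day 168, and 1.1% to 1.4% at day 28. The poorly determined directions largely cancel in the curve. Only predictions before day 7 are poor (16% to 91% at day 3).

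**The case against.** The strongest reply is that the text is open. The parameter list is illustrative, the analyses are to be done as needed, and section 9.5 announces a detailed SAP that will supersede the protocol. Naming an input model and bringing in outside data are ordinary SAP content, and nothing excludes the phase 1 data. This explains why the point is minor but does not answer it. Adding ka and F to the list would not help, because these data cannot estimate F or separate ka from Q, Vd1 and Vd2. Alpha half-life and Vdss are promised outright.

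The reply is stronger on consequences. A reader might infer three things that the documents do not support.

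- *That the concentration-risk analysis is undermined.* Section 8.2.3 uses the concentration at the visit before the first infection, which reads as a measured value, and section 9.5.6 does not say that model predictions will be the covariate. If they were, step 5 shows adequate precision from day 7, which is when the efficacy endpoint starts (section 9.5.4).
- *That a primary endpoint of the extension is compromised.* PK evaluation is a primary objective there, but the matching endpoint in sections 1.1 and 3 is measured serum L9LS, not a compartmental parameter. The individual non-compartmental analysis is also unaffected by this point.
- *That most PK information is lost, or that the fit will fail to converge.* CL/F and terminal half-life remain estimable, and part of the defect is a missing /F label. Non-convergence was not shown.

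**Conclusion.** Wrong as written, low severity. The paragraph commits to estimates that this design cannot produce.

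That CL, Vd1, Vd2, Q and Vdss are obtainable only relative to F rests on route alone and needs no assumed values. That Q/F, separate Vd1/F and Vd2/F, and alpha half-life are unreliable follows from the sampling times. The size given (23% to over 5,000%, above 100% in most scenarios) depends on assumed ka, Q, volumes and variances, and the most favourable scenario is far better than the rest. The good precision for CL/F relies on visits being spread over their windows or on a reduced model.

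Primary efficacy and safety analyses are untouched, and exposure from day 7 is not materially affected.

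**What to change.** Rewrite the population PK paragraph of section 9.5.6 to say that:

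1. the model has first-order subcutaneous absorption, and all clearances and volumes are apparent (/F);
2. the reported results are CL/F, V/F, terminal half-life and predicted concentrations from day 7;
3. alpha half-life, Q, separate Vd1 and Vd2, and Vdss are not reported as estimates from this trial alone;
4. a reduced model is used, or two compartments are kept only with external L9LS PK data as priors (phase 1 intravenous and subcutaneous data and, if available, the Mali paediatric subcutaneous data), with a sensitivity analysis.

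The sensitivity analysis is needed because only five adults received subcutaneous L9LS in phase 1 (section 2.3.1), and section 4.2.2 reports half-lives of about 55 to 65 days in adults against about 35 in Malian children. Adult values may not transfer. The bias of a reduced model was not tested here, so its fit to the day-7 samples should be checked.

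The cost is a change of wording and, if priors are used, access to data from the product's developer. No new samples or visits are needed. The downside is that fewer PK parameters are claimed from this trial.
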